1.0 Introduction

This statistical analysis plan (SAP) describes the statistical analysis for risankizumab Study M15-998 "A Phase 3, Randomized, Double-Blind Study Comparing Risankizumab to Placebo in Subjects with Active Psoriatic Arthritis Including Those Who Have a History of Inadequate Response or Intolerance to Biologic Therapy(ies)." It provides details to further elaborate statistical methods as outlined in the protocol and describes analysis conventions to guide the statistical programming work.

Pharmacokinetics/pharmacodynamics, pharmacogenetic, and selected biomarkers will be analyzed separately and are not included in this SAP.

Unless noted otherwise, all analyses will be performed using SAS version 9.4 or later (SAS Institute Inc., Cary, NC 27513) under the UNIX operating system.

2.0 Study Background

2.1 Objectives

Primary Objective

Period 1 Double-blind

To compare the efficacy of risankizumab 150 mg versus placebo for the treatment of signs and symptoms of PsA in the study population.

Secondary Objectives

Period 1 Double-blind

To compare the safety and tolerability of risankizumab 150 mg versus placebo in the study population.

Period 2 Open-label

To evaluate the long-term safety, tolerability and efficacy of risankizumab 150 mg in subjects who have completed Period 1.

[figure not shown]
2.2 Study Design

This is a Phase 3, global, multi-center study that will evaluate moderately to severely active PsA patients. The subject population will consist of no more than 50% with an inadequate response (lack of efficacy after a minimum 12 weeks duration of therapy) or intolerance to 1 or 2 biologic therapies (Bio-IR). The remaining study population will be subjects who have an inadequate response (lack of efficacy after a minimum 12 weeks duration of therapy) or intolerance to at least 1 conventional synthetic disease modifying anti-rheumatic drugs (csDMARDs).

The study consists of a Screening Period (approximately 35 days), Period 1, Period 2 and a 20-week Follow-up Period. Period 1 is a 24-week randomized, double-blind, placebo-controlled, parallel-group period. Period 2 starts at Week 24. To maintain the blind to the original treatment allocation, treatment at Week 24 will be blinded: subjects randomized to placebo will receive blinded risankizumab 150 mg, and subjects randomized to risankizumab will receive blinded placebo. At Week 28 and for the remaining dosing visits (up to Week 208), all subjects will receive open-label risankizumab 150 mg every 12 weeks. Subjects will remain blinded to the original randomization allocation for the duration of study.

A schematic of the study is shown in [Figure 1](#).

Figure 1. Study Schematic

LEGEND:

BL = Baseline; RCT = randomized clinical trial; W = Week

* At Week 24, subjects randomized to placebo in Period 1 will receive a blinded dose of risankizumab. Subjects randomized to risankizumab treatment in Period 1 will receive a blinded dose of placebo.

** At Week 28, subjects randomized to placebo in Period 1 will receive a 2nd dose of risankizumab. Subjects randomized to risankizumab in Period 1 will receive risankizumab (scheduled dose).

*** From Week 40 and up to Week 208 Visits, doses occur q12w.

† Follow up phone call.

↑ Dosing.

◆ Bilateral radiographs of hands and feet if required for CASPAR criteria.

a. At Week 16, subjects classified as non-responders (defined as not achieving at least a 20% improvement in either or both tender joint count [TJC] and swollen joint count [SJC] at both Week 12 and Week 16) compared to Baseline will add or modify rescue concomitant medications/therapy as described in Section 5.4 of the study protocol. Rescue therapy qualification occurs only at Week 16 Visit.

b. Starting at Week 36, subjects classified as non-responders will be discontinued from study drug. See Section 5.5 of the study protocol for details.

The Primary Analysis will be conducted after all ongoing subjects have completed Week 24 and an interim database lock (Week-24 Database Lock) has occurred, to support an interim CSR for the initial regulatory submission. An additional interim database lock will be conducted to provide further efficacy and safety exposure for integrated summaries of efficacy and safety supporting the initial regulatory submission; no interim

CSR will be generated based on the second interim lock. After then, additional interim analyses may be conducted as deemed appropriate. The final analysis will be performed after all ongoing subjects complete the study.

2.3 Treatment Assignment and Blinding

Subjects will be randomized to risankizumab 150 mg or placebo in a 1:1 ratio.

Randomization will be stratified by current use of csDMARD (0 vs ≥ 1), number of prior biologic therapies (0 vs ≥ 1), and extent of psoriasis ($\geq 3\%$ BSA or $< 3\%$ BSA).

2.4 Sample Size Determination

Approximately 420 subjects will be randomized to risankizumab 150 mg or placebo in a ratio of 1:1 (210 subject/treatment group). A sample size of 210 in each group will have approximately 90% power to detect a difference in HAQ-DI mean change from baseline of 0.24 assuming that the common standard deviation is 0.72 using a two group t-test with a 0.05 two-sided significance level and accounting for a 10% dropout rate. This sample size also ensures that analyses will have at least a 90% power to detect a 20% treatment difference, with the placebo response rate seen in the previous Phase 2b study of 35.7%, in ACR20 at Week 24 using a two-sided test at a 0.05 significance level and accounting for a 10% dropout rate.

3.0 Endpoints

3.1 Primary Endpoint

The primary endpoint is ACR20 response at Week 24.

3.2 Secondary Endpoints

The following is a list of ranked secondary endpoints with multiplicity adjustment:

1. Change from Baseline in Health Assessment Questionnaire-Disability Index (HAQ-DI) score at Week 24;

2. Psoriasis Area Severity Index (PASI) 90 response at Week 24 (for subjects with BSA \geq 3% at Baseline);
3. ACR20 response at Week 16;
4. Minimal Disease Activity (MDA) response at Week 24;
5. Change from baseline in 36-Item Short Form Health Survey (SF-36) Physical Component Summary (PCS) score at Week 24;
6. Change from baseline in Functional Assessment of Chronic Illness Therapy-Fatigue (FACIT-Fatigue) score at Week 24.

Other secondary endpoints are:

1. ACR50 response at Week 24;
2. ACR70 response at Week 24;
3. Resolution of enthesitis defined as Leeds Enthesitis Index (LEI = 0) at Week 24 (for subjects with baseline presence of enthesitis (LEI > 0));
4. Resolution of dactylitis defined as Leeds Dactylitis Index (LDI = 0) at Week 24 (for subjects with baseline presence of dactylitis (LDI > 0)).

3.3 Additional Efficacy Endpoints

The primary and secondary efficacy endpoints are listed in Section 3.1 and Section 3.2, respectively. Additional efficacy endpoints at all scheduled visits (when measurements are collected) are listed below.

- ACR20/50/70 response;
- Change from Baseline in individual components of ACR response:
 - Change from Baseline in Tender Joint Count (TJC) (0 - 68);
 - Change from Baseline in Swollen Joint Count (SJC) (0 - 66);

- Change from Baseline in Physician Global Assessment of Disease Activity (PGA) (mm on a 100-mm horizontal visual analogue scale [VAS]);
- Change from Baseline in Patient's Global Assessment of Disease Activity (PtGA) (mm on a 100-mm horizontal visual analogue scale [VAS]);
- Change from Baseline in Patient's Assessment of Pain (mm on a 100-mm horizontal visual analogue scale [VAS]);
- Change from Baseline in Health Assessment Questionnaire - Disability Index (HAQ-DI) score;
- Change from Baseline in High-Sensitivity C Reactive Protein (hs-CRP);
- MDA response;
- Change from Baseline in LDI (for subjects with Baseline LDI > 0);
- Change from Baseline in dactylitis count (for subjects with Baseline LDI > 0);
- Resolution of dactylitis (LDI = 0) (for subjects with Baseline LDI > 0);
- Change from Baseline in LEI (for subjects with Baseline LEI > 0);
- Resolution of enthesitis (LEI = 0) (for subjects with Baseline LEI > 0);
- Change from Baseline in Spondyloarthritis Research Consortium of Canada (SPARCC) Enthesitis Index (for subjects with baseline SPARCC Enthesitis Index > 0);
- Resolution of enthesitis sites included in the SPARCC Enthesitis Index (for subjects with Baseline SPARCC Enthesitis Index > 0);
- Change from Baseline in total enthesitis count (for subjects with baseline LEI > 0 and Baseline SPARCC Enthesitis Index > 0);
- Resolution of enthesitis in both LEI and SPARCC (defined as LEI = 0 and SPARCC = 0) (for subjects with Baseline LEI > 0 and Baseline SPARCC Enthesitis Index > 0);
- PASI 75/90/100 response (for subjects with BSA \geq 3% at Baseline);
- Achievement of both PASI 90 and ACR50 (for subjects with BSA \geq 3% at Baseline);
- Change from Baseline in BSA-PsO (for subjects with BSA \geq 3% at Baseline);
- Modified Psoriatic Arthritis Response Criteria (PsARC);

- Change from Baseline in Disease Activity Score 28 using high sensitivity C Reactive Protein (DAS28-hsCRP);
- Change from Baseline in PsA Disease Activity Score (PASDAS);
- Change from Baseline in Disease Activity in Psoriatic Arthritis (DAPSA) score;
- Change from Baseline in FACIT-Fatigue score;
- Change from Baseline in SF-36 physical component summary, mental component summary and the 8 sub-domain scores;
- Change from Baseline in EuroQol-5D-5L (EQ-5D-5L) index and VAS scores;
- Change from Baseline in Work Productivity and Activity Impairment (WPAI) measures;
- Health resource utilization (HRU) since last study visit;
- Change from Baseline in Bath Ankylosing Spondylitis Disease Activity Index (BASDAI) score (for subjects with spondylitis at Baseline, for subjects with spondylitis at Baseline confirmed by radiography or MRI);
- Change from Baseline in modified BASDAI score (for subjects with spondylitis at Baseline, for subjects with spondylitis at Baseline confirmed by radiography or MRI);
- Change from Baseline in BASDAI – Spinal Pain (for subjects with spondylitis at Baseline, for subjects with spondylitis at Baseline confirmed by radiography or MRI);
- BASDAI50 response (for subjects with spondylitis at Baseline, for subjects with spondylitis at Baseline confirmed by radiography or MRI);
- Change from Baseline in morning stiffness score (mean of BASDAI Questions 5 and 6) (for subjects with spondylitis at Baseline, for subjects with spondylitis at Baseline confirmed by radiography or MRI);
- Change from Baseline in Ankylosing Spondylitis Disease Activity Score (ASDAS) (for subjects with spondylitis at Baseline and for subjects with spondylitis at Baseline confirmed by radiography or MRI);
- ASDAS Inactive Disease (for subjects with spondylitis at Baseline and for subjects with spondylitis at Baseline confirmed by radiography or MRI);

- ASDAS Major Improvement (for subjects with spondylitis at Baseline and for subjects with spondylitis at Baseline confirmed by radiography or MRI);
- ASDAS Clinically Important Improvement (for subjects with spondylitis at Baseline and for subjects with spondylitis at Baseline confirmed by radiography or MRI);
- Achievement of a clinically meaningful improvement in HAQ-DI defined as $\Delta\text{HAQ-DI} \leq -0.35$ (for subjects with $\text{HAQ-DI} \geq 0.35$ at Baseline).

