3.4 Additional Endpoints

Additional endpoints at the scheduled time points as indicated in [Appendix D](#):

- Proportion of subjects achieving ACR20, ACR50, or ACR70 response;
- Change from Baseline in individual components of ACR response;
- Change from Baseline in LDI in subjects with dactylitis at Baseline;
- Change from Baseline in dactylitis count in subjects with dactylitis at Baseline;
- Proportion of subjects with resolution of dactylitis sites included in the LDI in subjects with dactylitis at Baseline;
- Change from Baseline in LEI in subjects with enthesitis in the LEI at Baseline
- Proportion of subjects with resolution of enthesitis sites included in the LEI in subjects with enthesitis in the LEI at Baseline;
- Change from Baseline in Spondyloarthritis Research Consortium of Canada (SPARCC) Enthesitis Index in subjects with enthesitis in the SPARCC at Baseline;
- Proportion of subjects with resolution of enthesitis sites included in the SPARCC Enthesitis Index in subjects with enthesitis in the SPARCC at Baseline;
- Change from Baseline in total enthesitis count in subjects with enthesitis in the LEI or SPARCC at Baseline;
- Proportion of subjects with resolution of enthesitis in LEI and SPARCC in subjects with enthesitis in the LEI or SPARCC at Baseline;
- Proportion of subjects achieving PASI 75 response (in the subset of subjects with a BSA \geq 3% at Baseline);
- Proportion of subjects achieving PASI 90 response (in the subset of subjects with a BSA \geq 3% at Baseline);
- Proportion of subjects achieving PASI 100 response (in the subset of subjects with a BSA \geq 3% at Baseline);

- Proportion of subjects with both ACR 50 and PASI 90 response (in the subset of subjects with a BSA \geq 3% at Baseline)
- Change from Baseline in BSA-PsO (in the subset of subjects with a BSA \geq 3% at Baseline);
- Proportion of subjects who achieve a Modified Psoriatic Arthritis Response Criteria (PsARC) response;
- Change from Baseline in Disease Activity Score 28 using high sensitivity C-Reactive Protein (DAS28-hsCRP);
- Change from Baseline in PsA Disease Activity Score (PASDAS);
- Change from Baseline in Disease Activity In Psoriatic Arthritis (DAPSA) score;
- Change from Baseline in FACIT-Fatigue Questionnaire;
- Change from Baseline in SF-36 Health Questionnaire;
- Change from Baseline in EuroQoL-5D-5L (EQ-5D-5L) Health Questionnaire;
- Change from Baseline in Work Productivity and Activity Impairment (WPAI) Questionnaire;

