APPENDIX H. LEEDS DACTYLITIS INDEX

The LDI basic measures the ratio of the circumference of the affected digit to the circumference of the digit on the opposite hand or foot, using a minimum difference of 10% to define a dactylitic digit.^{7,8} The ratio of circumference is multiplied by a tenderness score, using a modification of LDI which is a binary score (1 for tender, 0 for non-tender). If both sides are considered involved, or the circumference of the contralateral digit cannot be obtained, AbbVie will input and utilize a circumference provided in the standard reference tables. This modification is referred to as LDI basic and will be applied in this study. The LDI requires a finger circumference gauge or a tape measure to measure digital circumference.

Dactylitis Count

The dactylitis count is the number of fingers and toes with dactylitis, with a range of 0 – 20.

Presence of Dactylitis

If dactylitis is present with any finger or toe, the subject is counted as a subject with dactylitis.

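### The SAP's LDI > 0 filter leaves subjects whose dactylitic digits are all non-tender out of the dactylitis-count endpoint and the baseline dactylitis rows, which the protocol's own definition would include

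*SAP*

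**What the plan says.** Operations Manual Appendix H (part of Protocol Appendix F) sets three definitions.

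- A digit is dactylitic by size, "using a minimum difference of 10% to define a dactylitic digit".
- The dactylitis count is the number of such fingers and toes, from 0 to 20.
- At subject level, "If dactylitis is present with any finger or toe, the subject is counted as a subject with dactylitis".

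Tenderness enters only in the index. The circumference ratio is "multiplied by a tenderness score, using a modification of LDI which is a binary score (1 for tender, 0 for non-tender"), and "This modification is referred to as LDI basic and will be applied in this study".

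Protocol 3.4 gives the count endpoint as "Change from Baseline in dactylitis count in subjects with dactylitis at Baseline". SAP 3.3 gives it as "Change from Baseline in dactylitis count (for subjects with Baseline LDI > 0"). SAP 7.1 defines the baseline row for presence of dactylitis as LDI > 0 and restricts the baseline summary of total dactylitis count to those same subjects.

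SAP 3.2 has, as an unranked secondary endpoint, "Resolution of dactylitis defined as Leeds Dactylitis Index (LDI = 0) at Week 24", among subjects with baseline LDI > 0. Protocol 3.3 also defines resolution as LDI = 0.

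**The concern.** The SAP treats LDI > 0 as the operational form of having dactylitis at Baseline. Under the scoring in Appendix H, LDI > 0 means something narrower: at least one dactylitic digit that is also tender. The two documents therefore attach different populations to the same words.

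The mismatch matters most for the dactylitis count, which ignores tenderness. Filtering a swelling-based count by a tenderness-weighted index removes subjects who have a positive baseline count and could show a change in it. In the baseline table the same subjects would be recorded as having no dactylitis, so the reported prevalence would not match the protocol's definition. At stake is whom one additional endpoint and two baseline rows describe, together with some loss of sample in a subgroup.

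**Working it through.** The documents state no figure for this endpoint, so there is none to reproduce. The check applies the Appendix H rules to example subjects.

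**Inputs from the documents**
- A digit is dactylitic if affected / contralateral circumference ≥ 1.10 (Appendix H).
- Tenderness score t = 1 if tender, 0 if not (Appendix H). Operations Manual 3.5 has it recorded yes or no for affected digit pairs, after they have been identified by inspection and measured. An affected, non-tender digit is therefore a possible record.
- Count = number of dactylitic digits.
- LDI = sum over dactylitic digits of ratio × t.

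Appendix H does not spell out how digits are combined, so the sum is my assumption. It does not affect the zeros: if every t is 0, every contribution is 0. The same holds if the index is scored as the excess over a reference value.

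**Example subjects** (circumferences are illustrative)

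| Subject | Digits | LDI | Count | Dactylitis by Appendix H | SAP filter LDI > 0 |
|---|---|---|---|---|---|
| A | one digit, 66 vs 60 mm, non-tender | 1.10 × 0 = 0 | 1 | yes | excluded |
| B | three digits, 72 vs 60 mm, none tender | 3 × (1.20 × 0) = 0 | 3 | yes | excluded |
| C | three digits, 72 vs 60 mm, one tender | 1.20 × 1 + 1.20 × 0 + 1.20 × 0 = 1.20 | 3 | yes | included |

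A and B belong to the Protocol 3.4 population but not to the SAP 3.3 population. In SAP 7.1 they are counted as having no dactylitis. C shows the limit of the problem, since one tender digit is enough for inclusion.

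**Comparison with enthesitis.** In the same SAP 7.1 list, total enthesitis count is summarised in subjects with total enthesitis count > 0, that is, a count filtered by itself. For the LEI an index filter would also work, because Appendix I scores each site by tenderness, so LEI > 0 and presence of enthesitis at LEI sites coincide. For the LDI they do not. The Operations Manual recognises the difference elsewhere: the PASDAS formula in Appendix M uses a separate tender dactylitis count.

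**Where LDI > 0 is the right filter.** A subject with baseline LDI = 0 cannot improve on the LDI and already meets LDI = 0. For change in LDI and for LDI = 0 resolution, restricting to LDI > 0 is the coherent choice.

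**The case against.** The best defence is that the SAP exists to make the protocol operational. It does so with one rule, printed beside each dactylitis item and applied throughout. Appendix H's sentence on presence of dactylitis describes the instrument and does not expressly name an analysis population. A common denominator for all dactylitis endpoints has some appeal. The consistency and transparency of the rule stand. However, neither document says that tender dactylitis was intended, and Appendix H is the only place where the protocol says who counts as a subject with dactylitis.

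Four stronger readings are tempting, and the documents do not support them.

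1. *The SAP wrongly counts still-swollen digits as resolved.* A digit that stays enlarged but is no longer tender does give LDI = 0. But Protocol 3.3 itself names LDI = 0 as the resolution endpoint, and the SAP follows it.
2. *Nothing would reveal residual swelling.* The count endpoint would, and in the same subjects as the resolution endpoint. If subject C still has three digits at 72 vs 60 mm at Week 24, none tender, LDI is 0 (resolved) but the change in count is 3 − 3 = 0.
3. *The treatment comparison is biased.* The filter uses a baseline variable and applies equally to both arms. It changes whom the estimate describes, not its validity within that group.
4. *The loss can be estimated.* Protocol 2.1 quotes a background prevalence of 8% to 59%, and 420 × 0.08 = 33.6 while 420 × 0.59 = 247.8. Assuming that 5% to 30% of these have no tender dactylitic digit gives 33.6 × 0.05 = 1.7 up to 247.8 × 0.30 = 74.3. That share has no source in the documents, and the result spans more than fortyfold. The upper end, about 124 subjects with dactylitis per arm, also sits poorly with the rationale in Protocol Appendix E, which un-ranked this endpoint because the subpopulation was expected to be too small for adequate power.

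**Conclusion.** The point holds as a small inconsistency between the SAP and the protocol. It is limited to one additional endpoint (change in dactylitis count) and two baseline rows (presence of dactylitis and total dactylitis count). In those places LDI > 0 leaves out subjects whose dactylitic digits are all non-tender, although Appendix H and Protocol 3.4 include them.

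The conclusion rests on reading Appendix H literally: size alone makes a digit dactylitic, and tenderness is only a multiplier in the index. The number affected is unknown and could be very small. The count endpoint carries nominal p-values only (SAP 8.5). The primary endpoint, the ranked sequence, alpha and sample size are unaffected.

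**What to change.** - In SAP 3.3, define the population for change in dactylitis count as baseline dactylitis count > 0.
- In SAP 7.1, use the same rule for the presence-of-dactylitis row and for the total dactylitis count row.
- Report how many subjects in each arm have count > 0 with LDI = 0 at baseline, so that the two denominators can be reconciled.
- Keep LDI > 0 for change in LDI and for the LDI = 0 resolution endpoint.
- Optionally, add a supplementary table with resolution defined as count = 0 among subjects with baseline count > 0.

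The cost is SAP wording and one extra line of counts, plus one table if the optional analysis is taken up. Circumference and tenderness are already collected by digit, so no data collection changes.

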An assessment of 66 joints will be done by directed physical examination. The hip joints are not assessed for swelling; all other joints that are assessed for tenderness will also be assessed for swelling. Joint swelling will be classified as present, absent, replaced, or no assessment. Joints injected with corticosteroid will be considered non-evaluable for 90 days from the time of the injection.

The assessor should be an independent qualified medical professional.

Dactylitis

LDI

This evaluation will be conducted to assess the presence or absence of dactylitis in all 20 of the subject's digits. The assessment should begin with visual inspection of the hands and feet. For each pair of digits in which one or both digits appear dactylitic, the circumference of the affected digits (both right and left side) will be assessed using a dactylometer. Additionally, the affected digit pairs will be assessed for tenderness by squeezing the digital shaft mid-way between the metacarpophalangeal and proximal interphalangeal joints and will be recorded as tenderness, yes or no. Tenderness should not be assessed by squeezing the joint lines. Digits injected with corticosteroid will be considered non-evaluable for 90 days from the time of the injection. If a digit is missing and its contralateral digit is dactylitic, "digit

absent" will be recorded for the missing digit. For any digit without an available dactylometer measurement, the standard reference value will be utilized in calculation of the LDI. The standard reference values will not be entered into the eCRF. A dactylometer will be provided to sites for use.

The assessor should be an independent qualified medical professional.

Enthesitis

LEI

LEI is a validated enthesitis index that uses 6 sites for evaluation of enthesitis: lateral epicondyle humerus left and right, Achilles tendon insertion left and right, and medial condyle femur left and right. Tenderness on examination is recorded as either present, absent, or not assessed for each of the 6 sites, for an overall score range of 0 – 6.

Enthesitis sites injected with corticosteroid will be considered non-evaluable for 90 days from the time of the injection.

The assessor should be an independent qualified medical professional.

SPARCC Enthesitis Index

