This evaluation will be conducted to assess the presence or absence of enthesitis at 8 bilateral sites: medial epicondyle, lateral epicondyle, supraspinatus insertion to the greater tuberosity of the humerus, greater trochanter, quadriceps insertion into the superior border of the patella, patellar ligament insertion into the inferior pole of the patella or tibial tubercle, Achilles tendon insertion into calcaneum, and plantar fascia insertion into calcaneum. Tenderness on examination is recorded as either present, absent, or not assessed for each of the 16 sites. For scoring purposes, the inferior patella and tibial tuberosity are considered to be one site due to their anatomical proximity. The overall score range is 0 – 16. Enthesitis sites injected with corticosteroid will be considered non-evaluable for 90 days from the time of the injection. The lateral epicondyle and Achilles tendon insertion will only need to be assessed once since the 2 bilateral sites overlap between the LEI and SPARCC.

The assessor should be an independent qualified medical professional.

Psoriatic Spondylitis

This evaluation will be conducted at Baseline only as part of assessing PsA subtype. If the investigator determines that a subject has psoriatic spondylitis, how the diagnosis was made should be recorded (i.e., clinical evaluation, radiography and/or MRI).

Where possible, this evaluation should be assessed by a rheumatologist.

CASPAR

This is a validated set of criteria used for the classification of PsA based on the presence of inflammatory arthritis (joints, spine, or entheses) with ≥ 3 points from 5 categories as specified in [Appendix B](#).

Subjects may receive bilateral radiographs of the hands and feet if needed to determine whether the subject fulfills item 5 of the CASPAR criteria ([Appendix B](#)). Radiographs will be locally read for CASPAR scoring.

PGA

Physician Global Assessment (PGA) of Disease Activity (VAS) allows physicians to score on a 100 mm horizontal scale (0 being very well and 100 being very poorly) to assess the patient's overall functionality assessment considering the disease activity within the past 24 hours.

The assessor is not required to be independent but should be a qualified medical professional, preferably a physician.

Investigator assessments are shown in [Appendix D](#) through [Appendix P](#).

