7.1 Demographics and Baseline Characteristics

The following demographic and baseline characteristics will be summarized.

Demographic Characteristics

- Sex (male, female)
- Age (years)
- Age Categories (< 65 years, ≥ 65 years, ≥ 65 and < 75 years, ≥ 75 years)
- Race (White, Black or African American, American Indian or Alaska Native, Native Hawaiian or Other Pacific Islander, Asian, Other)
- Geographic Region (North America, South/Central America, Western Europe, Eastern Europe, Asia, Other)
- Ethnicity (Hispanic or Latino, Not Hispanic or Latino)

- Weight (kg)
- Weight Categories (< 100 kg, ≥ 100 kg)
- Height (cm)
- Body Mass Index (BMI) (kg/m²)
- Body Mass Index (BMI) Category (kg/m²) (< 25, ≥ 25 and < 30, ≥ 30)

PsA Medical History and Prior and Concomitant Medications

- Duration of PsA in years
- Duration of PsA in years categories (≤ 5, > 5 and ≤ 10, > 10 years)
- Number of prior csDMARDs (0, 1, 2, ≥ 3)
- Number of prior biologics (0, ≥ 1)
- Number of prior failed biologics (0, 1, ≥ 2)
- Prior exposure to TNF antagonists (yes, no)
- Nonsteroidal anti-inflammatory drug (NSAID) use at Baseline (yes, no)
- Oral Corticosteroid use at Baseline (yes, no)
- Concomitant MTX use at Baseline (yes, no)
- Concomitant csDMARD at Baseline

Any csDMARD

- Any MTX
 - MTX alone
 - MTX and other csDMARD
- csDMARD other than MTX
 - Any sulfasalazine, without MTX
 - Any leflunomide, without MTX
 - Any apremilast, without MTX

None

Baseline Disease Characteristics

Categorical:

- Minimal Disease Activity (MDA) for PsA (yes, no)
- Presence of Dactylitis (LDI > 0) (yes, no)
- Presence of Enthesitis based on LEI (LEI > 0) (yes, no)
- Presence of Enthesitis based on SPARCC (SPARCC Enthesitis Index > 0) (yes, no)
- Body Surface Area (BSA) of psoriatic plaques ($\geq 3\%$, $< 3\%$)
- Presence of spondylitis (yes, no)
- Anti-cyclic citrullinated peptide (Anti-CCP) status (Positive (≥ 17 U/mL), Negative (< 17 U/mL))
- Rheumatoid Factor (RF) status (Positive (≥ 15 IU/mL), Negative (< 15 IU/mL))
- Categories for hsCRP (< 3.0 , ≥ 3.0 mg/L)

Continuous:

- Psoriasis Area and Severity Index (PASI) (for subjects with BSA $\geq 3\%$ at Baseline)
- Disease Activity Score in 28 joints – hsCRP (DAS28(CRP))
- Total dactylitis count (for subjects with presence of dactylitis (LDI > 0))
- LDI (for subjects with presence of dactylitis (LDI > 0))
- Total enthesitis count (for subjects with presence of enthesitis (total enthesitis count > 0))
- LEI (for subjects with LEI > 0)

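### SAP 3.3 analyses two combined enthesitis endpoints in subjects positive on both LEI and SPARCC, where Protocol 3.4 specifies subjects positive on either

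*SAP*

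**What the plan says.** Protocol Section 3.4 lists two endpoints that combine the enthesitis indices, and both use a union at Baseline. One is "Change from Baseline in total enthesitis count in subjects with enthesitis in the LEI or SPARCC at Baseline". The other, joint resolution on the two indices, is defined for that same group.

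SAP Section 3.3 lists the same two endpoints with an intersection. The change in the total count is to be analysed "for subjects with baseline LEI > 0 and Baseline SPARCC Enthesitis Index > 0". The second, resolution in both indices (defined there as LEI = 0 and SPARCC = 0), carries the same condition.

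SAP Section 7.1 describes the total count at Baseline in a different set: "Total enthesitis count (for subjects with presence of enthesitis (total enthesitis count > 0".

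The SAP's introduction presents the document as elaborating the protocol's methods. Its version history (Section 13.0) records no change to this population and gives no reason for one.

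**The concern.** The same two endpoints have different denominators in the two documents. A programmer following SAP 3.3 literally would exclude subjects whom the protocol includes. For the total count, the change-from-baseline analysis would also cover a different set from the SAP's own baseline summary of that variable. For resolution, some subjects who are unresolved at Baseline by the SAP's own definition would be left out.

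At stake are the size, precision and traceability of two additional endpoints. An unexplained difference also leaves room to choose the denominator later.

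**Working it through.** The documents state no figure to reproduce. The check compares the texts and then counts sites.

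**1. Which population fits the definitions?**

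| Place | Population |
|---|---|
| Protocol 3.4, both endpoints | LEI or SPARCC enthesitis |
| SAP 3.3, both endpoints | LEI > 0 and SPARCC > 0 |
| SAP 7.1, total count at Baseline | total count > 0 |

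Neither document gives a formula for the total count. Taking it as the tender sites across both indices, it exceeds zero exactly when LEI > 0 or SPARCC > 0, whether shared sites are counted once or twice. SAP 7.1 therefore matches the protocol.

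For resolution, the outcome state is LEI = 0 and SPARCC = 0. The subjects not in that state at Baseline are those with LEI > 0 or SPARCC > 0. A subject with LEI = 0 and SPARCC = 5 is unresolved and can resolve, yet SAP 3.3 excludes that subject. The SAP's single-index resolution bullets do use the matching complement: LEI = 0 among LEI > 0, LDI = 0 among LDI > 0, and SPARCC resolution among SPARCC > 0.

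**2. Who is dropped?** Inputs are from the Operations Manual (Protocol Appendix F), Section 3.5:

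- LEI has 6 sites: "LEI is a validated enthesitis index that uses 6 sites for evaluation of enthesitis".
- SPARCC has 8 × 2 = 16 sites: "presence or absence of enthesitis at 8 bilateral sites".
- Lateral epicondyle and Achilles insertion are shared on both sides, 2 × 2 = 4 sites. They "will only need to be assessed once since the 2 bilateral sites overlap between the LEI and SPARCC".

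Distinct sites: 6 + 16 − 4 = 18, made up of 4 shared, 6 − 4 = 2 LEI-only (medial femoral condyles) and 16 − 4 = 12 SPARCC-only.

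A subject in the protocol's set fails the SAP's rule if all tender sites are SPARCC-only (1 to 12 sites) or all are LEI-only (1 or 2 sites). One tender Achilles site keeps a subject in; 12 tender SPARCC-only sites do not.

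**3. How many?** The documents give no baseline distribution of tender sites, so the number of subjects cannot be computed. As an illustration, assume every pattern of k tender sites among the 18 is equally likely. The share dropped is [C(12,k) + C(2,k)] / C(18,k):

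| k | Patterns dropped | All patterns | Share |
|---|---|---|---|
| 1 | 12 + 2 = 14 | 18 | 77.8% |
| 2 | 66 + 1 = 67 | 153 | 43.8% |
| 3 | 220 | 816 | 27.0% |
| 4 | 495 | 3,060 | 16.2% |
| 5 | 792 | 8,568 | 9.2% |
| 6 | 924 | 18,564 | 5.0% |

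Without that assumption, the share for any k from 1 to 12 could lie anywhere from 0% (every subject has a shared site tender) to 100% (all tenderness at SPARCC-only sites). With 13 or more tender sites nobody is dropped.

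**The case against.** The best defence of 'and' is that the SAP (version 6.0, 16 November 2020) postdates the protocol (synopsis dated 10 September 2020), and that an index starting at zero has nothing to resolve, so requiring both to be positive is coherent. Neither document states which population was intended. The defence does not hold. The SAP makes resolution a joint state, so a subject positive on one index is unresolved and can resolve. The argument also does not reach the total count, where SAP 7.1 uses the wider set.

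Other points on that side do stand. SAP 3.3 analyses change and resolution for LEI in all subjects with LEI > 0 and for SPARCC in all with SPARCC > 0, so nobody dropped here is lost to enthesitis analysis altogether. Both endpoints are additional endpoints with nominal p-values only (SAP 8.5).

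A reader might infer more than the documents support:

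- *That the rule removes milder enthesitis.* Sites are scored present or absent, and exclusion depends on which sites are tender. Low counts are dropped more often only under the even-site assumption.
- *That it lowers the apparent resolution rate.* No resolution rates by count or site are given, so the direction is unknown.
- *That it biases the treatment comparison.* The rule uses Baseline status and applies equally to both randomised arms. Nothing in the documents shows bias.

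**Conclusion.** The SAP's population for these two endpoints departs without explanation from the protocol, and conflicts with the SAP's own baseline table and resolution definition. It is wrong as written. The analysed set is no larger than the protocol's and is probably smaller, with some loss of precision. The size of that loss is unknown: the shares from 78% at one tender site to 5% at six rest on the even-site assumption and are not forecasts of exclusions in this trial.

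The consequence is small. The primary endpoint, the ranked secondary endpoints, the alpha allocation and the sample size are unaffected. So is the unranked secondary endpoint of LEI resolution, which is already defined in subjects with LEI > 0. The mismatch itself is certain because it can be read directly from the two texts.

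**What to change.** In SAP 3.3, change 'and' to 'or' in the population clause of both bullets, so that each covers subjects with Baseline LEI > 0 or SPARCC > 0, that is, total enthesitis count > 0. Leave the outcome definition, LEI = 0 and SPARCC = 0, unchanged. In the same edit, state that the 4 shared sites count once in the total, since no formula for it is given.

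The cost is two words, one sentence and a line in the version history. No data collection, sample size or testing order changes. If the sponsor does want the narrower set, the SAP should say that it departs from Protocol 3.4 and why, and SAP 7.1 should describe the same set.
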